#### 6.2.2.9. *Treatment Visit 9 (Week 16 [Day 112 ±3 days])*

The treatment Visit 9 is planned on Day 112 ± 3 days in Week 16. Following activities are planned for the visit:

- Review and record patient's prior and concomitant medications
- Record patient's body weight
- Calculate BMI
- Perform symptom-directed physical examination
- Perform vital signs (systolic/diastolic BP, heart rate, temperature, respiratory rate) evaluation pre-dose
- Pruritus assessment
- AE monitoring
- Perform clinical laboratory analysis including haematology, serum chemistry panel, coagulation tests, lipid and metabolic profile and TSH.
- Perform urine pregnancy test (for WOCBP only)
- Perform Dipstick urinalysis for all male and female patients
- Perform 12-Lead ECG
- Sampling for analysis of HBV response markers
- PD biomarker sampling
- Liver fibrosis and inflammation assessment
- Perform Fibroscan VCTE
- PK Sampling
- Review returned patient diary and dispense new diary
- Dispense NA
- Collect used/unused study drug and assess compliance

#### 6.2.3. **Follow-up Period (Week 17 to Week 40)**

The study procedures during the follow-up period are allocated on Follow-up Visits 1 (Week 20 [Day 140 ± 7 days]), 2 (Week 28 [Day 196 ± 7 days]) and 3 (Week 40 [Day 280 ± 7 days]). The patients will be outpatient during the follow-up period. Please refer [Section 19.1](#) for overall activities planned for the follow-up period.

##### 6.2.3.1. *Follow-up Visit 1 (Week 20 [Day 140 ± 7 days])*

The follow-up Visit 1 is planned on Day 140 ± 3 days in Week 20. Following activities are planned for the visit:

- Review and record patient's prior and concomitant medications
- Record patient's body weight
- Calculate BMI
- Perform symptom-directed physical examination
- Perform vital signs (systolic/diastolic BP, heart rate, temperature, respiratory rate) evaluation pre-dose
- Pruritus assessment
- AE monitoring

- Perform clinical laboratory analysis including haematology, serum chemistry panel, coagulation tests and lipid and metabolic profile
- Sampling for analysis of HBV response markers
- PD biomarker sampling
- Liver fibrosis and inflammation assessment
- Review returned patient diary and dispense new diary
- Dispense NA
- Collect used/unused study drug and assess compliance

6.2.3.2. *Follow-up Visit 2 (Week 28 [Day 196 ± 7 days])*

The follow-up Visit 2 is planned on Day 196 ± 3 days in Week 28. Following activities are planned for the visit:

- Review and record patient's prior and concomitant medications
- Record patient's body weight
- Calculate BMI
- Perform symptom-directed physical examination
- Perform vital signs (systolic/diastolic BP, heart rate, temperature, respiratory rate) evaluation pre-dose
- Perform pruritus assessment
- AE monitoring
- Perform clinical laboratory analysis including haematology, serum chemistry panel, coagulation tests and lipid and metabolic profile
- Sampling for analysis of HBV response markers
- PD biomarkers sampling
- Liver fibrosis and inflammation assessment
- Review returned patient diary and dispense new diary
- Dispense NA
- Collect used/unused study drug and assess compliance

6.2.3.3. *Follow-up Visit 3/EoS Visit (Week 40 [Day 280 ± 7 days])*

The follow-up Visit 3/EoS Visit is planned on Day 280 ± 3 days in Week 40. Following activities are planned for the visit:

- Review and record patient's prior and concomitant medications
- Record patient's body weight
- Calculate BMI
- Perform symptom-directed physical examination
- Perform vital signs (systolic/diastolic BP, heart rate, temperature, respiratory rate) evaluation pre-dose
- Perform pruritus assessment
- AE monitoring
- Perform clinical laboratory analysis including haematology, serum chemistry panel, coagulation tests and lipid and metabolic profile
- Sampling for analysis of HBV response markers
- PD biomarkers sampling
- Liver fibrosis and inflammation assessment

- Perform Fibroscan VCTE
- Review returned patient diary
- Collect used/unused study drug and assess compliance
- Perform liver imaging to screen patient for HCC. For patients with risk factors for HCC, i.e. any of these: family history with HCC, >40 years of age, male sex, born in Sub-Saharan Africa, Metabolic syndrome (obesity, diabetes), smoking, ALT>ULN, HBV DNA (>2,000 IU/mL), HBeAg-negative, Genotype C) during follow-up phase liver imaging is also performed at week 40.

#### **6.2.4. Early Termination (ET) Visit**

The ET Visit is planned for patients who discontinue early from the study for any reason, for a follow-up approximately one week after administration of their final last dose of any study medication, regardless of how many days the patient was in the study. Please refer [Section 19.1](#) for the collection of data based on the following activities planned for the visit:

- Review and record patient's prior and concomitant medications
- Record patient's body weight
- Calculate BMI
- Perform symptom-directed physical examination
- Perform vital signs (systolic/diastolic BP, heart rate, temperature, respiratory rate)
- Pruritus assessment
- AE monitoring
- Perform clinical laboratory analysis including haematology, serum chemistry panel, coagulation tests and lipid and metabolic profile
- Perform serum pregnancy test (for WOCBP only)
- Perform Dipstick urinalysis for all male and female patients
- Perform 12-Lead ECG
- Sampling for analysis of HBV response markers
- PD biomarker sampling
- Liver fibrosis and inflammation assessment
- Perform Fibroscan VCTE
- PK sampling
- Review returned patient diary
- Collect used/unused study drug and assess compliance

#### **6.3. Appropriateness of Measurements**

Standard efficacy, PK, PD, statistical, clinical and laboratory procedures will be utilized in this study.

## **7. Efficacy Variables**

The efficacy of EYP001a will be assessed via the following efficacy variables:

## 7.1. Definitions

### Primary efficacy variables

The primary efficacy variables are:

- HBsAg decline ( $\Delta \log_{10}$ ) from Day 1 to Week 16 of treatment period

### Secondary efficacy variables

The secondary efficacy variables are as follows:

- HBsAg responder rate (decrease from baseline  $\geq 1.0$  on the  $\log_{10}$  scale) at Week 16 of treatment and Weeks 20, 28 and 40 of follow up.
- HBsAg responder rate (decrease from baseline  $\geq 0.5$  on the  $\log_{10}$  scale) at Weeks 12 and 16 of treatment and Weeks 20, 28 and 40 of follow up.
- HBsAg loss rate (% patients with HBsAg < LLOQ) at Weeks 16 of treatment period and Weeks 20, 28 and 40 of follow-up.
- HBsAg loss rate (proportion of results that are Target Not Detected versus Target Detected) at Weeks 16 of treatment period and Weeks 20, 28 and 40 of follow-up.
- relapse rate HBsAg (% patients who became negative [HBsAg < LLOQ], then increased with HBsAg > LLOQ) at Week 16 of treatment period and Weeks 20, 28 and 40 during follow-up period.
- Virologic failure rate (breakthrough) of HBV DNA (% patients with a confirmed quantifiable HBV DNA increase of  $\geq 1 \log_{10}$  HBV DNA copies/mL above LLOQ) assessed at Week 16 of treatment period and Weeks 20, 28 and 40 during follow-up period
- HBV pgRNA decline ( $\Delta \log_{10}$ ) from Day 1 to Weeks 4, 8, 12 and 16 of treatment period and Week 40 of maintenance period
- HBcrAg decline ( $\Delta \log_{10}$ ) from Day 1 to Weeks 4, 8, 12 and 16 of treatment period and Week 40 of maintenance period
- HBeAg quantification for HBeAg pos patients and changes at Week 16 of treatment and Week 40 of follow-up
- Fibroscan VCTE change from screening to Weeks 16 and 40 or ET

Analysis of HBV response markers:

- Samples for analysis of quantitative HBsAg and quantitative HBV-DNA will be collected at pre-dose on all study visits during treatment period and Weeks 20, 28 and 40 of follow-up or at the ET visit.
- Samples for analysis of quantitative HBV pgRNA and HBcrAg will be collected at pre-dose on all study visits during treatment period and Week 40 of maintenance during follow-up period or at the ET visit.

---

 Breakthrough samples will be further assessed for resistance assessments, including both for the nucleos(t)ide analogue as well as for EYP001a (e.g., sequence analysis of FXR response elements in HBV genome). Details will be described in the Laboratory manual.

 HBV DNA results <LLOQ will be reported as either <LLOQ/Detected (i.e. LLOQ/TD) or <LLOQ/Target Not Detected (i.e. LLOQ/TND), both are considered LLOQ.

- Sample for analysis of HBeAg, anti-HBe and anti-HBs will be collected at screening or Day 1, then pre-dose at Week 16, Week 40 (EoS visit) or ET Visit.

## 7.2. Drug Concentration Measurements

The analysis of IP (EYP001a) in serum samples, as well as the analysis of biomarkers, will be performed at a Bioanalytical Laboratory using validated or qualified methods. The bioanalytical reports for the determinations will be included in the clinical study report (CSR).

## 8. Safety Assessments

The safety and tolerability of EYP001a will be assessed throughout the study.

Safety and tolerability will be determined by evaluating medical history (including evaluation of AEs and concomitant medication use) and assessments will include the monitoring of adverse events (AEs) and Serious Adverse Events (SAEs), and findings from physical examinations, vital signs, 12-lead ECGs, and clinical laboratory parameters.

**Clinical laboratory** assessments will include:

- **Haematology:** red blood cell count, white blood cell count and differential; quantitatively - leukocytes, erythrocytes, haemoglobin, haematocrit; partial automated differentiation - thrombocytes, lymphocytes, monocytes, eosinophils, basophils, neutrophils, and platelets.  
**Coagulation:** quantitatively - prothrombin time (reported in seconds and as INR), activated partial thromboplastin time, and fibrinogen
- **Serum chemistry:** ALT, albumin, ALP, amylase, AST, blood urea nitrogen, calcium, creatine kinase, creatinine phosphokinase (CPK), creatinine, Estimation of glomerular filtration rate, GGT, glucose, lactate dehydrogenase, potassium, sodium, total bilirubin (if >ULN, add conjugated bilirubin), total protein, uric acid.
- **Additional chemistry:** Alpha 2 macroglobulin, autotaxin, cardiac troponin I, ferritin, phosphate and TSH. These markers will be assessed at the end of study on existing chemistry plasma aliquots collected on Day 1, Day 112 and Day 280, only if relevant improvements in liver inflammation or fibrosis are apparent.
- **Lipid and metabolic profiles:** branched-chain amino acid concentrations as liver function test, haemoglobin A1c, homeostatic model assessment for insulin resistance (morning fasting glucose and insulin), lipoprotein insulin resistance index by nuclear magnetic resonance based on serum cholesterol, HDL-C, LDL-C, triglycerides, apolipoprotein B, small dense LDL, and lipoprotein(a).  
Lipoprotein particle size; small LDL particle number, small very low-density lipoprotein (VLDL) particle number, VLDL size
- **Urinalysis (dipstick qualitatively):** bilirubin, nitrite, blood, pH, glucose, protein, haemoglobin, specific gravity, ketones, urobilinogen, and leukocytes);
- **Pregnancy testing.**

Laboratory parameters combined with AE, ECG and clinical assessments will be established at each study visit. They are considered appropriate measures for the following reasons:

- EYP001a Phase 1 studies showed pharmacological effects related to target FXR engagement as expected in the digestive system and lipid metabolism. From the available data no off-target effect has been evidenced. No dose-related or clinically significant changes in haematology or clinical chemistry laboratory values were evidenced so far.
- The study population will be adequately monitored through ECG, the safety lab, in particular liver enzymes, CPK, and cardiac troponin I, which aids in the risk stratification of patients with potentially unstable angina or non-ST segment elevation acute coronary syndromes with increased probability of ischemic events requiring urgent revascularization procedures.
- Patients with cirrhotic liver disease are excluded from this study.

### **8.1. Adverse Events and Adverse Event Reactions**

**Adverse Event (AE):** Any untoward medical occurrence in a subject or clinical investigation subject administered a pharmaceutical product and which does not necessarily have to have a causal relationship with this treatment.

An AE can therefore be any unfavourable and unintended sign (including an abnormal laboratory finding, for example), symptom or disease temporally associated with the use of a medicinal product, whether or not considered related to the medicinal product.

**Adverse Drug Reaction (ADR):** In the pre-approval, clinical experience with a new medicinal product or its new usages, particularly as the therapeutic dose(s) may not be established: all noxious and unintended responses to a medicinal product related to any dose should be considered ADRs.

The phrase "responses to a medicinal products" means that a causal relationship between a medicinal product and an AE is at least a reasonable possibility, i.e., the relationship cannot be ruled out.

**Unexpected ADR:** An adverse reaction, the nature and severity of which is not consistent with the applicable product information (e.g. IB for an unapproved medicinal product).

#### **8.1.1. Recording of Adverse Events**

All AEs during the course of the trial will be reported in the appropriate section in the eCRF. The investigator will give his or her opinion as to the relationship of the adverse event to the investigational product. The Investigator should attempt to establish a diagnosis of the AE based on signs, symptoms, and/or other clinical information. In such cases, the diagnosis should be documented as the AE verbatim term rather than individual signs/symptoms.

All AEs regardless of relationship to the study drug during the period starting from the time the participant signed the ICF through 7 days after the last study drug dose will be recorded in the eCRF.

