### 3. Study Plan

#### 3.1. Description of Overall Study Design and Plan

This is a prospective, multi-centre, randomized, double-blind, placebo controlled, Phase 2a experimental study of oral FXR modulator EYP001a/placebo combined with NA in virologically suppressed CHB patients to improve functional cure rates.

---

 Breakthrough samples will be further assessed for resistance assessments, including both for the nucleos(t)ide analogue as well as for EYP001a (e.g., sequence analysis of FXR response elements in HBV genome). Details will be described in the Laboratory manual.

 HBV DNA results <LLOQ will be reported as either <LLOQ/Detected (i.e. LLOQ/TD) or <LLOQ/Target Not Detected (i.e. LLOQ/TND), both are considered LLOQ.

In total 49 eligible patients will be enrolled and randomized at approximately 14 study sites. Patients will be randomized prior to study drug (EYP001a or placebo and NA) administration on Day 1 in the ratio of 3:1 into 2 arms:

- **Experimental Arm:** EYP001a 200 mg QD + NA daily (37 patients)
- **Control Arm:** Placebo + NA daily (12 patients)

[figure not shown]
Patients will also be stratified per HBeAg status, based on medical history HBeAg value or established during screening, to obtain a balanced randomization to both study arms.

The maximum total engagement duration for eligible patients in this study is up to 370 days: 90 days screening, 112 days (16 weeks) treatment period and 168 days (24 weeks) follow-up.

Patients enrolled in the study will be assessed as outpatients. Patient screening will occur no more than 90 days prior to the Day 1 visit. Eligible patients will undergo further assessments on Day 1 to qualify for study drug administration on Day 1.

A diagrammatic representation of the study design is presented in [Figure 7](#):

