**Figure 7 Study Design**

The visits during the study are planned as below:

- Screening visit: 12 weeks (90 days)
- 16 weeks treatment period:
  - Treatment Visit 1 (Week 1 [Day 1])
  - Treatment Visit 2 (Week 2 [Day 14 ± 3 days])
  - Treatment Visit 3 (Week 4 [Day 28 ± 3 days])
  - Treatment Visit 4 (Week 6 [Day 42 ± 3 days])
  - Treatment Visit 5 (Week 8 [Day 56 ± 3 days])
  - Treatment Visit 6 (Week 10 [Day 70 ± 3 days])
  - Treatment Visit 7 (Week 12 [Day 84 ± 3 days])
  - Treatment Visit 8 (Week 14 [Day 98 ± 3 days])
  - Treatment Visit 9 (Week 16 [Day 112 ± 3 days])
- 24 weeks safety follow-up period:
  - Follow-up Visit 1 (Week 20 [Day 140 ± 7 days])
  - Follow-up Visit 2 (Week 28 [Day 196 ± 7 days])
  - Follow-up Visit 3 (Week 40 [Day 280 ± 7 days])

Note: during follow-up patients are kept on NA until the end of the trial: Week 40

- (consolidation Phase).
- Post study consolidation period: after Week 40, the investigator can continue or stop NA therapy provided the following recommended plan is respected at the end of the study: after cessation of antiviral therapy, there is a transition of HBV care to a local provider for continued monitoring every 3 months with clinical and ALT/AST assessments for at least one year to monitor eventual HBV flares.

Please refer to [Section 6](#) for planned assessments/activities at each study visit.

Safety, tolerance, PK /PD and efficacy of EYP001a will be established in an outpatient setting. An external, independent Data Safety Monitoring Committee (DSMC) will review all available unblinded preliminary virology, safety, PK and PD results when any stopping rules ([Section 4.6](#)) are met in two or more subjects and on two occasions for a scheduled interim analysis. Please refer to [Section 3.3](#) for details.

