### **5.11. Treatment Compliance**

The study drug (EYP001a/Placebo and NA) will be dispensed to the patients by the Investigator or study site personnel dedicated to the study on the treatment visits 1, 3, 5, 7 and 9 (for EYP001a/Placebo dispensation is only at visits 1 and 5, as each boxe is for 8 weeks of treatment). Please note 16 weeks of treatment (EYP001a/Placebo and NA) with 8 weeks treatment units will be dispensed. Should the patient "loose" treatment units the check on sufficient treatment can be made at each fortnightly visit. Patient diary will be provided on the treatment visits 1, 2, 3, 4, 5, 6, 7, 8 and 9. NA will also be dispensed along with patient diary, on the follow up visits 1 and 2. Patients will administer the study drug (EYP001a/placebo and NA) outside the study sites (at home) during the treatment period (Week 1 to Week 16) and follow-up period (Week 17 to Week 40) as instructed by Investigator or study-site personnel and will record the dosing details in the patient diary to document compliance.

Data pertaining to tablet count for the study drug will be collected on the treatment visits 2, 3, 4, 5, 6, 7, 8 and 9; on all follow-up visits and on ET visit. If a patient's drug administration and site-related procedures are not conducted as defined in the protocol, the Investigator will make note of ensuring compliance to the protocol for future activities.

The date and time of each study drug administration and accompanying activity recorded in the patient diary will be transcribed in the eCRF. Detailed instructions for the dispensing instructions of EYP001a are described in the study pharmacy manual.

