### 8.2.2. Reporting of Serious Adverse Events

All SAEs regardless of relationship to the study drug during the period starting from the time the patient signed the ICF through 7 days after the last study drug dose, will be

recorded in the eCRF. Once the Investigator becomes aware of an SAE, he/she must report the SAE to the Sponsor safety representative within 24 hours of knowledge of the event.

Safety Contact Information:

Pharmalex:

[contact]

[contact]

Email: [contact]

A written SAE report must include a full description of the event including the below parameters (include any protocol specific requirements):

- Diagnosis or description of event
- Onset date
- Severity assessment
- Causal relationship to the investigational product
- Assessment of seriousness of the event
- Corrective treatment administered for the SAE
- Action taken related to study drug include the following: dose interruption, dose delay, dose reduction, or study drug discontinuation
- Outcome of event and end date

Follow-up information for SAEs and information on non-serious AEs that become serious should also be reported to Sponsor Safety representative within 24 hours of receipt of follow-up information.

The Investigator must update the SAE form and submit any supporting documentation (eg, patient discharge summary or autopsy reports) to the ENYO safety designee via fax or email.

The Investigator is responsible for reporting all SAEs to the appropriate Institutional Review Board/Institutional Ethics Committee (IRB/IEC) in accordance with local laws and regulations. The Investigator is responsible for maintaining documentation in the study file that indicates the IRB/IEC has been properly notified.

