13.1 Adverse Events

All AEs including will be coded using MedDRA. All AE summaries will be restricted to TEAEs only. Summary tables will include the number of participants (%) experiencing an event and the number of events. Participants will be counted only once for each SOC and PT level (categorical descriptive analysis).

AE and SAE will be analysed taking into account any identified subject with Sars-Cov2 infection during and post-pandemic measures phases. Such an analysis will be operated through the independent Data Monitoring Committee (DMC).

The TEAE summaries will include:

- Overall summary of TEAEs.
 - Number of TEAEs
 - Number of TEAEs with Severity \geq Grade 3 Severe
 - Number of Serious TEAEs
 - Number of Study Drug Related TEAEs (Drug Related: A Possibly, Probably or Definitely related TEAE)
 - Number of Entecavir (ETV) Related TEAEs (Drug Related: A Possibly, Probably or Definitely related TEAE)
 - Number of Tenofovir Disoproxil Fumarate (TDF) Related TEAEs (Drug Related: A Possibly, Probably or Definitely related TEAE)
 - Number of TEAEs leading to study drug withdrawal
- TEAE summary by SOC and PT.
- TEAE summary of serious events by SOC and PT.
- TEAE summary by SOC, PT and Severity.
- TEAE summary by SOC, PT and relationship to study drug.
- TEAE summary by SOC, PT and relationship to ETV.
- TEAE summary by SOC, PT and relationship to TD.
- TEAE summary of events leading to the study drug discontinuation by SOC and PT.

All AEs will be listed and will include verbatim term, PT, SOC, treatment, causality to study drug, ETV and TDF, severity, seriousness, outcome, and action taken with regards to the study drug and AE. Separate listings will be created for SAEs and events leading to study drug withdrawal.

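### AE and SAE recording ends 7 days after the last dose of 'study drug', a term used in two senses: one leaves up to 161 days of follow-up uncovered, the other none

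*Protocol*

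**What the plan says.** **The cut-off.** Protocol 8.1.1 records AEs, whatever their relationship to treatment, from consent "through 7 days after the last study drug dose will be recorded in the eCRF". Protocol 8.2.2 repeats the limit for SAEs: "through 7 days after the last study drug dose".

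**The opposing sentence.** The same section 8.1.1 opens without any limit: "All AEs during the course of the trial will be reported in the appropriate section in the eCRF". Section 8.2.2 has no such opening.

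**The calendar.** Protocol 3.1 gives "112 days (16 weeks) treatment period and 168 days (24 weeks) follow-up", and the visit list under Figure 7 labels the second part as "24 weeks safety follow-up period". After Week 16 patients take NA only.

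**Study drug as EYP001a/placebo only.**
- Protocol 5.1.3 offers Table 2 as the full description of the study drug; its product columns are EYP001a and placebo.
- Protocol 4.6 includes rule 8 among its study drug stopping criteria. That rule stops EYP001a/placebo while NA goes on, or is changed, at the investigator's discretion.
- SAP 8 handles study drug administration and NA administration separately.
- SAP 13.1 counts "Number of Study Drug Related TEAEs" separately from events related to entecavir or to tenofovir.
- The mock listing of AEs leading to study drug withdrawal selects on the action taken with EYP001a/placebo.

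**Study drug as EYP001a/placebo plus NA.**
- Protocol 5.11: "The study drug (EYP001a/Placebo and NA) will be dispensed". The section goes on to say that patients take it through the follow-up period.
- Protocol 3.1, Appendix A footnotes 20 to 22, and SAP 2.1 and 2.5 spell the term out in the same way.

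**The concern.** A recording window has to close on the same day at every site. Here the closing day depends on a term that the protocol's safety sections do not define and that the two documents use in both senses. A site that takes the sense used in Table 2 and in the SAP's AE outputs would stop recording new events about a week after Week 16. A site that takes the sense in 5.11 would continue to the end of the study.

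The rest of the plan expects events to Week 40. AE monitoring is listed at Weeks 20, 28 and 40 in Protocol 6.2.3 and in Appendix A. The TEAE definition in SAP 3.2 has a start but no end. All-cause mortality is a safety endpoint, and concomitant medication is collected to the end-of-study or early termination visit.

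At stake is whether AE and SAE counts after Week 16 are complete and comparable. There are about 14 sites and 12 planned controls, so a few sites with an early cut-off could change the picture. An event that was never recorded may not be recoverable later.

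**Working it through.** **Inputs**
- Last planned EYP001a/placebo dose: about Day 112 (Treatment Visit 9, Day 112 ± 3).
- End-of-study visit: Day 280 (Follow-up Visit 3, Day 280 ± 7).
- Other follow-up visits: Days 140 and 196, each ± 7.
- Recording tail: 7 days (Protocol 8.1.1 and 8.2.2).
- Last NA dose: about Day 280. This is an assumption, based on patients being kept on NA to Week 40.

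**The plan's own figures.** 90 + 112 + 168 = 370 days of maximum engagement; 112 + 168 = Day 280; 168 / 7 = 24 weeks. All three agree with Protocol 3.1.

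**Formula.** Window end = day of last dose + 7. Uncovered time = end-of-study day − window end, or zero if that is negative.

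| Sense of *study drug* | Window end | Uncovered at nominal days |
|---|---|---|
| EYP001a/placebo only | 112 + 7 = Day 119 | 280 − 119 = 161 days |
| EYP001a/placebo plus NA | 280 + 7 = Day 287 | 0 days |

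**Size under the narrow sense**
- 161 / 7 = 23.0 weeks.
- 161 / 168 = 95.8% of the follow-up period.
- 161 / 280 = 57.5% of Days 1 to 280.
- Follow-up visits after the cut-off: Days 140, 196 and 280, which is all three.

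**Allowing for visit windows**
- The window end ranges from 109 + 7 = Day 116 to 115 + 7 = Day 122.
- Shortest gap: 273 − 122 = 151 days (21.6 weeks). Longest gap: 287 − 116 = 171 days (24.4 weeks).
- The earliest possible first follow-up visit is 140 − 7 = Day 133, still after Day 122. No follow-up visit can fall inside the narrow window.

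These figures are for patients who complete 16 weeks. For a patient who stops EYP001a/placebo early but stays in the study on NA, the narrow cut-off moves earlier by the same number of days.

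**Does another rule close the gap?** Protocol 8.1.2 and 8.2.3 follow events until resolution, stabilization or 30 days after study completion. They govern the follow-up of events and do not extend the window for recording new ones.

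**The case against.** The case for the broad sense is substantial. Protocol 3.1 and 5.11, the Appendix A footnotes and SAP 2.1 and 2.5 all put NA inside the parentheses when they spell the term out. Protocol 5.11 has patients taking study drug from Week 17 to Week 40. The follow-up visit lists collect used and unused study drug at Weeks 20, 28 and 40, when only NA is being taken. The 7-day tail also fits the early termination visit, set about a week after the last dose of any study medication. Stopping rule 8 names EYP001a or placebo rather than study drug at the point where it separates the products, and Protocol 8.3 never says that NA continues. An SAE is also an AE, so the opening sentence of 8.1.1 arguably covers SAEs.

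Much of this stands. It shows that the broad sense is a fair reading and that loss of data is not established. It does not show that the documents have chosen that sense: Table 2, SAP 8 and SAP 13.1 use the narrow one, and the narrow one underlies the AE outputs. The schedule shows that AEs are asked about at follow-up visits; it does not say whether it overrides the explicit 7-day limit.

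A reader might infer more: that AE collection does stop at Day 119, or that off-drug flares and virological breakthrough would go unseen. The documents support neither. The early stop follows from one reading only. HBV DNA and liver chemistry are sampled at Weeks 20, 28 and 40 whatever the AE window. Breakthrough is a prespecified endpoint at those visits, and SAP 13.2 summarizes maximum CTCAE grades for ALT and AST and plots HBV DNA against both.

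**Conclusion.** The point holds as a conflict between stated rules built on an undefined term. If *study drug* means EYP001a/placebo only, up to 161 days (23 weeks) at nominal visit days and every follow-up visit lie outside the recording window; if it includes NA, nothing does. The 161 days are therefore the most a completing patient could lose at nominal days, not an expected loss. The figure assumes a last EYP001a/placebo dose at about Day 112.

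The practical risk is that sites apply different cut-offs. It falls mainly on clinical AEs and SAEs that scheduled laboratory sampling would not show. It is somewhat sharper for SAEs, because 8.2.2 repeats the limit without the sentence that softens it in 8.1.1.

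It would go too far to say that the SAP as a whole uses the narrow sense: its AE and exposure sections do, while 2.1 and 2.5 do not. Protocol 8.3 does not define the term either way. The point should be corrected, because the possible loss is in safety data and the remedy is small.

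**What to change.** Reconcile the sentences in Protocol 8.1.1 and 8.2.2 with the opening of 8.1.1, the follow-up visit schedule and the TEAE definition in SAP 3.2, by either route:

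1. End AE and SAE recording at the Week 40/end-of-study visit, or at the early termination visit for those who leave early.
2. Keep the 7-day tail, and state that the last dose means the last dose of EYP001a/placebo or of NA, whichever is later.

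In both cases, give *study drug* one definition and use it in the protocol's safety sections and the SAP's AE sections. Where only EYP001a/placebo is meant, as in the separate causality counts, name it.

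The cost is two sentences and one definition. No visit, sample or assessment is added, because AE monitoring is already scheduled at Weeks 20, 28 and 40.
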